4.5.13 Acute Exacerbations of COPD

All patients will be provided with a diary to track daily study treatment and the date(s) of any AEx events. Patients will be required to bring their diaries to study visits. Patients will be asked if they have experienced an AEx during the last month at each study visit.

The investigator will ask directed questions to assess whether the patient experienced any adverse events and any protocol-defined COPD exacerbations since the last study visit.

Given that COPD exacerbations are the key primary endpoint in this study, a dedicated eCRF will be used to record information regarding protocol-defined exacerbation events. A COPD exacerbation must also be reported as an adverse event (or serious adverse event as applicable) as per Section [5.2](#). Sites should update the COPD Targeted Concomitant Medications eCRF with all medications used for treatment.

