2.2 SAFETY OBJECTIVE

The safety objective for this study is to evaluate the safety of ^{129}Xe MRI procedures and of AZM+SOC compared with SOC on the basis of the following endpoints:

- Incidence and severity of adverse events, with severity determined according to the World Health Organization (WHO) toxicity scale
- Change from baseline in targeted vital signs
- Change from baseline in targeted clinical laboratory test results
- Change from baseline in ECG data

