3. STUDY DESIGN

3.1 DESCRIPTION OF THE STUDY

This is a multicenter, open-label, parallel group, randomized study designed to assess the sensitivity of HP ^{129}Xe MRI metrics as measures of disease progression in patients with COPD treated with SOC medications with or without daily azithromycin treatment. MRI with inhaled HP ^{129}Xe gas (^{129}Xe MRI) will be evaluated as a diagnostic tool that may provide useful images of the functioning of the lung for determining changes in lung function and structure. Approximately 120 patients with a diagnosis of COPD will be enrolled in the study across two cohorts (defined by severity of disease) and three arms. Patients will be followed for 52 weeks, during a 48-week open-label treatment period followed by a 4-week safety follow-up period, with assessments performed at baseline and at Weeks 6, 12, 24, and 48. ^{129}Xe MRI images will be compared with standard lung function assessments, including 6MWT to assess functional status, quantitative HRCT to assess lung structure, and questionnaires to assess shortness of breath and quality of life. Patients will be enrolled in the following cohorts:

- **Cohort A:** Approximately 100 patients with COPD GOLD Stage 2–4 (GOLD 2–4), with or without chronic bronchitis, and history of ≥ 2 AEx within a 12-month period in the prior 24 months will be randomly assigned in a 1:1 ratio to the following treatment arms:
 - AZM + SOC: azithromycin (250 mg QD) plus other SOC therapy consisting of LABAs and/or LAMAs, with or without ICS therapy
 - SOC: SOC therapy consisting of LABAs and/or LAMAs, with or without ICS therapy
 Randomization will be stratified by region (United States vs. United Kingdom/Canada) and by the number of exacerbations in the prior 12 months (2 vs. ≥ 3).
- **Cohort B:** Approximately 20 patients with COPD GOLD Stage 1 (GOLD 1), with or without chronic bronchitis, and history of ≥ 1 AEx within a 12-month period in the prior 24 months will be enrolled as an observational cohort into the following arm:
 - SOC: SOC therapy consisting of LABAs and/or LAMAs, with or without ICS therapy

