5.3.1 Adverse Event Reporting Period

Investigators will seek information on adverse events at each patient contact. All adverse events, whether reported by the patient or noted by study personnel, will be recorded in the patient's medical record and on the Adverse Event eCRF.

After informed consent has been obtained but prior to initiation of study randomization, only serious adverse events caused by a protocol-mandated intervention (e.g., invasive procedures such as biopsies, discontinuation of medications) should be reported (see Section 5.3.2 for instructions for reporting serious adverse events).

After randomization, all adverse events will be reported until 28 days after the final dose of azithromycin.

Instructions for reporting adverse events that occur after the adverse event reporting period are provided in Section 5.5.

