5.3.2 Eliciting Adverse Event Information

A consistent methodology of non-directive questioning should be adopted for eliciting adverse event information at all patient evaluation timepoints. Examples of non-directive questions include the following:

"How have you felt since your last clinic visit?"

"Have you had any new or changed health problems since you were last here?"

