5.6 ADVERSE EVENTS THAT OCCUR AFTER THE ADVERSE EVENT REPORTING PERIOD

The Sponsor should be notified if the investigator becomes aware of any serious adverse event that occurs after the end of the adverse event reporting period (defined as 28 days after the final dose of study drug), if the event is believed to be related to prior study treatment. These events should be reported through use of the Adverse Event

¹²⁹Xe MRI—Genentech, Inc.

66/Protocol GE42063, Version 5

eCRF. However, if the EDC system is not available, the investigator should report these events directly to the Sponsor or its designee, either by faxing or by scanning and emailing the paper Clinical Trial Serious Adverse Event/Adverse Event of Special Interest Reporting Form using the fax number or email address provided to investigators.

5.7 EXPEDITED REPORTING TO HEALTH AUTHORITIES, INVESTIGATORS, INSTITUTIONAL REVIEW BOARDS, AND ETHICS COMMITTEES

The Sponsor will promptly evaluate all serious adverse events and adverse events of special interest against cumulative product experience to identify and expeditiously communicate possible new safety findings to investigators, IRBs, ECs, and applicable health authorities based on applicable legislation.

To determine reporting requirements for single adverse event cases, the Sponsor will assess the expectedness of these events through use of the reference safety information in the documents listed below:

Drug	Document
Azithromycin	Single drug covered by prescribing information: Azithromycin E.U. Summary of Product Characteristics
¹²⁹ Xe MRI	Drug device combination covered by combination Investigator's Brochure: HP ¹²⁹ Xe and MRI Investigator's Brochure

HP = hyperpolarized; MRI = magnetic resonance imaging.

The Sponsor will compare the severity of each event and the cumulative event frequency reported for the study with the severity and frequency reported in the applicable reference document.

Reporting requirements will also be based on the investigator's assessment of causality and seriousness, with allowance for upgrading by the Sponsor as needed.

A SMC will monitor the incidence of the above-listed anticipated events during the study. An aggregate report of any clinically relevant imbalances that do not favor the test product will be submitted to health authorities.

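### Section 4.5.13 has adverse events sought by directed questions, Section 5.3.2 by a consistent non-directive method at the same visits, and nothing in the protocol reconciles the two

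*Combined protocol and SAP*

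**What the plan says.** Section 4.5.13, on acute exacerbations, instructs: "The investigator will ask directed questions to assess whether the patient experienced any adverse events and any protocol-defined COPD exacerbations" since the previous visit. The exacerbation half of that sentence rests on a protocol definition and a dedicated eCRF. The adverse event half has neither wording nor a list of items.

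Section 5.3.2, the section on eliciting adverse events, says: "A consistent methodology of non-directive questioning should be adopted for eliciting adverse event information at all patient evaluation timepoints". Its examples are open questions, such as "Have you had any new or changed health problems since you were last here". It makes no exception for Section 4.5.13.

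On timing, Section 5.3.1 says: "Investigators will seek information on adverse events at each patient contact".

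On use, Section 2.2 lists first among the safety endpoints: "Incidence and severity of adverse events, with severity determined according to the World Health Organization (WHO) toxicity scale". The objective there compares AZM + SOC with SOC, and Section 6.5 groups patients by treatment received. Section 3.1 states: "This is a multicenter, open-label, parallel group, randomized study".

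One directed query is specified separately. Section 4.5.5 has Cohort A patients, without distinction of arm, asked about new or worsening hearing loss and hearing disturbances. Appendix 1 footnote bb, attached to the adverse event row, adds a hearing query only for those randomized to azithromycin.

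**The concern.** How a patient is asked affects which symptoms get reported. An open question collects what the patient volunteers; a directed one collects what the questioner thought to name. A single non-directive method used everywhere makes counts comparable across sites and arms. Here a site can cite the protocol for either method.

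Two things are at stake. First, with about 7 sites, some may work from 4.5.13 and others from 5.3.2, so that patient-reported event rates vary by site for reasons unrelated to treatment. Second, because the directed questions are unscripted, their content is left to staff who know the assignment and who have the azithromycin risks of Section 5.1.2 in front of them. That leaves room for more probing in one arm than in the other. Nothing in the protocol says this will happen, but 4.5.13 weakens the instruction that would guard against it.

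**Working it through.** No arithmetic applies: the protocol gives no adverse event rates and no capture probabilities by method of questioning. The check is a side-by-side reading.

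1. **Same data?** Yes. Section 4.5.13 names adverse events in general, alongside exacerbations. Section 5.3.2 covers adverse event information in general.

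2. **Same occasions?** Yes. Section 4.5.13 asks about the interval since the previous visit, so it applies visit by visit. Section 5.3.2 covers all evaluation timepoints, and 5.3.1 covers every contact.

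3. **Anything that reconciles them?** None found. Neither section cites the other. No text puts open questions before directed ones, confines the directed questions to exacerbations, or says which section governs.

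4. **Is the clash intended?** It does not look so. Section 4.5.14 shows the clean form: directed questions limited to urgent COPD-related health care, with their own eCRF. Section 4.5.13 would match it if adverse events were not named in the sentence.

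5. **Which endpoints are exposed?** Events that come to light by asking the patient. Section 2.2 also lists laboratory, vital-sign and ECG changes, which depend little on interview style.

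6. **What follows for the arm comparison?**
 - If a site uses one method for all its patients, the method itself favours neither arm. It adds variation between sites. Section 4.2 stratifies by region and exacerbation history, without listing site, so balance of arms within a site is expected on average but not forced.
 - If the directed questions differ by arm within a site, the comparison is biased. Section 4.5.13 neither prescribes nor prevents this.

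7. **Is any arm asymmetry actually written down?** Yes, in one place. Under footnote bb the azithromycin arm receives a hearing query that the SOC arm does not; under Section 4.5.5 both Cohort A arms are queried. If footnote bb is read as additional to 4.5.5, the azithromycin arm is asked more often. If it is read as replacing 4.5.5, only that arm is asked. On either reading, hearing events found this way are not ascertained equally in the two arms.

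**The case against.** The best case on the other side is that this is loose drafting. Section 5.3.2 is the section devoted to eliciting adverse events, so a sensible site would let it govern. Open questions followed by directed ones are feasible in one visit, so the instructions are not strictly impossible to combine. Section 5.3.2 also says only that the method should be adopted. Part of this stands: the conflict is one clause, and a careful site could work around it. But the protocol does not give that sequence, and directed adverse event questions added at some sites would still break the consistency that 5.3.2 asks for. The verbs do not help either, since 4.5.13 says the investigator will ask directed questions, which is the firmer wording.

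A second objection stands in full. Section 4.5.13 makes no distinction by arm, and selective probing by unblinded staff is a risk of the open-label design under either wording. A reader might infer that the conflict biases the safety comparison against azithromycin, or inflates the chance of a false safety signal. The documents do not support that. Any figure would need invented reporting rates and an assumption that directed questions are used in effect only in one arm. Section 6.5 plans descriptive summaries, and Section 6.1 puts the focus on estimation, so there is no adverse event test whose error rate could be inflated.

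A reader might also infer that the frequency comparison with reference documents in Section 5.7 is distorted. That is weak: the comparison is set up to determine reporting requirements for single cases, and follows text on serious events and events of special interest. The one listed event of special interest is liver injury defined by laboratory values or jaundice.

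Lastly, Section 4.5.13 requires exacerbations to be reported as adverse events too, so directed questions will still feed that category after any correction. This is true and acceptable, because exacerbations are defined, have their own eCRF and can be shown separately.

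**Conclusion.** The inconsistency is certain and rests on the text alone. Its consequence is limited: patient-reported adverse events may be ascertained differently between sites, and the protocol leaves room for uneven questioning by staff who know the arm. Neither the size nor the direction of a between-arm difference can be derived from the documents. Bias between arms requires the further assumption that questioning differs by arm; only the hearing query shows such a difference in writing. Safety is not the primary objective, and laboratory, ECG and vital-sign endpoints are little affected. The point still deserves correction rather than a note, because it decides how a stated safety endpoint is collected.

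**What to change.** 1. In Section 4.5.13, remove adverse events from the sentence on directed questions, so that it covers only protocol-defined exacerbations since the previous visit.

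2. Add a sentence there saying that adverse events are elicited with the open questions of Section 5.3.2, in the same way for all patients, before the directed exacerbation and health care questions.

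3. Flag events that came to light through a separately specified directed query, and show them apart from the others in the Section 6.5 summaries.

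4. Reconcile Section 4.5.5 with Appendix 1 footnote bb on who receives the hearing query and when. Which version is right is a clinical decision for the sponsor. If the query remains limited to one arm, the safety summaries should say that hearing events found through it are not comparable between arms.

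The cost is one clause, a cross-reference, a line in site training and a marker on the adverse event record. Slightly fewer minor events may be reported than under directed questioning. Directed capture of exacerbations is unchanged.

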4.5.14 Urgent COPD-Related Health Care Utilization

At each study visit after randomization, the investigator will ask directed questions to assess whether the patient has required any urgent COPD-related health care since the last study visit. Urgent COPD-related health care utilization includes any hospitalizations, emergency department visits, and acute care visits (i.e., unplanned clinic visits). A dedicated eCRF will be used to record information regarding any COPD-related hospitalizations, emergency department visits, and/or acute care visits.

4.5.15 Six-Minute Walk Test

The 6MWT will be conducted as per the study 6MWT procedural manual that is based on the 2002 ATS guidelines for the 6MWT (ATS Statement 2002).

For safety reasons, all patients should be clinically stable prior to performing any study-related 6MWT. Supplemental oxygen flow rate will be recorded before every

6MWT. Heart rate, SpO₂, and the Borg Category-Ratio 10 (CR10) Scale[®] (Appendix 6) will be recorded immediately before and after the procedure. The Borg CR10 Scale is a 1-item assessment that can be used to measure a variety of perceptions and experiences (i.e., perceived exertion, chest pain, dyspnea, and fatigue) (Borg and Borg 2010). The Borg CR10 Scale ranges from 0 (Nothing at all) to 10 (Absolute maximum/Highest possible).

4.5.16 BODE Index

The BODE index is a composite score of other assessments collected in the study.

Body mass index (B), obstruction (O) as measured by FEV₁, dyspnea (D) as measured by the mMRC scale, and exercise endurance (E) as measured by the 6MWT will be assessed as described under the separate sections for each assessment. The standard scoring system will be followed (Celli et al. 2004).

4.5.17 Sputum Induction

Sputum induction will be performed per the study procedure manual. Patients will be pre-medicated with a bronchodilator and then inhale an aerosolized saline solution delivered by an ultrasonic nebulizer to facilitate forcible coughs and sputum expectoration. Peak expiratory flow and FEV₁ will be monitored during sputum induction for safety. Induced sputum will be processed immediately according to the lab manual at the clinical sites to obtain raw and sputolysin-treated sputum samples, as well as sputum cell pellets prepared in a special RNA-protecting solution.

4.5.18 Laboratory, Biomarker, and Other Biological Samples

Samples for the following laboratory tests will be sent to the study site's local laboratory for analysis:

- Hematology: WBC count, RBC count, hemoglobin, hematocrit, platelet count, and differential count (neutrophils, eosinophils, basophils, monocytes, lymphocytes, other cells)
- Chemistry: sodium, potassium, chloride, bicarbonate, glucose, BUN, creatinine, calcium, phosphorus, magnesium, total and direct bilirubin, total protein, albumin, ALT, AST, LDH, alkaline phosphatase, creatine phosphokinase, and uric acid
- Pregnancy test

All women of childbearing potential will have a serum pregnancy test at screening. Urine pregnancy tests will be performed at specified subsequent visits. If a urine pregnancy test is positive, it must be confirmed by a serum pregnancy test.

- Urinalysis, if clinically indicated as determined by the investigator, including dipstick (pH, specific gravity, glucose, protein, ketones, blood) and microscopic examination (which may include sediment, RBCs, WBCs, casts, crystals, epithelial cells, bacteria)

Samples for the following laboratory tests will be sent to the Sponsor or a designee for analysis:

- Serum and plasma samples for exploratory research on biomarkers
- Sputum samples for mucin measurements and for exploratory research on biomarkers

Exploratory biomarker research may include, but will not be limited to, analysis of eosinophils, neutrophils, sputum mucins, RNA expression from blood, and single nucleotide polymorphisms (SNPs) of selected genes (e.g., *FAM13A*, *ATF6*, and other genes related to COPD). Research will not be aimed at distinguishing germline mutations from somatic mutations.

For sampling procedures, storage conditions, and shipment instructions, see the laboratory manual.

Unless the patient gives specific consent for his or her leftover samples to be stored for optional exploratory research (see Section 4.5.22), biological samples will be destroyed when the final Clinical Study Report has been completed, with the following exception:

- Blood, serum, plasma, and sputum samples collected for biomarker research will be destroyed no later than 10 years after the final Clinical Study Report has been completed.

When a patient withdraws from the study, samples collected prior to the date of withdrawal may still be analyzed, unless the patient specifically requests that the samples be destroyed or local laws require destruction of the samples. However, if samples have been tested prior to withdrawal, results from those tests will remain as part of the overall research data.

Data arising from sample analysis, including data on germline mutations, will be subject to the confidentiality standards described in Section 8.4.

Given the complexity and exploratory nature of exploratory biomarker analyses, data derived from these analyses will generally not be provided to study investigators or patients unless required by law. The aggregate results of any conducted research will be available in accordance with the effective Sponsor policy on study data publication.

4.5.19 Electrocardiograms

Single ECG recordings will be obtained at specified timepoints, as outlined in the schedule of activities (see [Appendix 1](#)), and may be obtained at unscheduled timepoints as indicated.

All ECG recordings must be performed using a standard high-quality, high-fidelity digital electrocardiograph machine equipped with computer-based interval measurements. Lead placement should be as consistent as possible. ECG recordings must be

performed after the patient has been resting in a supine position for at least 10 minutes. All ECGs are to be obtained prior to other procedures scheduled at that same time (e.g., vital sign measurements, blood draws) and should not be obtained within 3 hours after any meal. Circumstances that may induce changes in heart rate, including environmental distractions (e.g., television, radio, conversation) should be avoided during the pre-ECG resting period and during ECG recording.

For safety monitoring purposes, the investigator must review, sign, and date all ECG tracings. Paper copies of ECG tracings will be kept as part of the patient's permanent study file at the site. The following should be recorded in the appropriate eCRF: time of day of recording, heart rate, RR interval, QRS interval, PR duration, uncorrected QT interval, and QT interval corrected through use of Fridericia's formula (QTcF) based on the machine readings of the individual ECG tracings. Any morphologic waveform changes or other ECG abnormalities must be documented on the eCRF. If considered appropriate by the Sponsor, ECGs may be analyzed retrospectively at a central laboratory.

If at a particular postdose timepoint the mean QTcF is >500 ms and/or >60 ms longer than the baseline value, another ECG must be recorded, ideally within the next 5 minutes, and ECG monitoring should continue until QTcF has stabilized on two successive ECGs. The Medical Monitor should be notified. Standard-of-care treatment may be instituted per the discretion of the investigator. The investigator should also evaluate the patient for potential concurrent risk factors (e.g., electrolyte abnormalities, co-medications known to prolong the QT interval, severe bradycardia).

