4.3.2 Study Treatment Dosage, Administration, and Compliance

The treatment regimens are summarized in Section 3.1. Details on treatment administration (e.g., dose and timing) should be noted on the Study Drug Administration electronic Case Report Form (eCRF). Guidelines for treatment interruption or

discontinuation for patients who experience adverse events are provided in Section 5.1.3.

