5.1.3.2 Treatment Interruption

Study treatment may be temporarily suspended in patients who experience toxicity considered to be related to study drug. If study treatment has been withheld for two or more consecutive dosing visits because of toxicity, the patient should be discontinued from study treatment. However, if the adverse event(s) that led to withholding dosing shows clear evidence of improvement in the investigator's judgment, treatment may be resumed; the Medical Monitor may be consulted as appropriate.

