5.1.3.3 Management Guidelines

Guidelines for management of specific adverse events are outlined in [Table 1](#).

Table 1 Management Guidelines

Event	Action to Be Taken
Hepatotoxicity	
ALT or AST $>3 \times$ ULN in combination with total bilirubin $>2 \times$ ULN or clinical jaundice	
 Immediately discontinue study treatment. Elevations of AST or ALT of $>5 \times$ ULN should be reported as adverse event(s) of special interest to the Sponsor in an expedited manner (see Section 5.3.3). A hepatology consult is recommended.
Hearing Disturbances	
Any reported onset hearing loss, worsening hearing loss, or hearing disturbance	
 Discontinue study treatment. Refer for formal audiology testing.
QT Prolongation	
Sustained (at least two ECG measurements >30 minutes apart) QTcF that is >500 ms and >60 ms longer than the baseline value	
 Unless there is a clear alternative cause other than study drug, discontinue study treatment (see Section 5.1.3.4).^a
Sustained absolute QTcF that is >515 ms	
 Unless there is a clear alternative cause other than study drug, discontinue study treatment (see Section 5.1.3.4).^a
An episode of torsades de pointes or a new ECG finding of clinical concern	
 Unless there is a clear alternative cause other than study drug, discontinue study treatment (see Section 5.1.3.4).^a

ULN=upper limit of normal.

^a In rare circumstances, it may be acceptable to resume azithromycin, provided that any ECG abnormalities have resolved and the patient is appropriately monitored, following discussion with the Medical Monitor. Clinical judgment should be applied.

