5.1.3.4 Management of Increases in QT Interval

Azithromycin should be discontinued in patients who develop any of the following, unless there is a clear alternative cause for the changes:

- Sustained absolute (at least two ECG measurements >30 minutes apart) QTcF that is >500 ms and >60 ms longer than the baseline value
- Sustained absolute QTcF that is >515 ms
- An episode of torsades de pointes or a new ECG finding of clinical concern

- Of note, if there is a new intraventricular conduction block, the increase in QRS complex duration should be subtracted from the QTcF change, because this represents an increase in QTcF unrelated to alterations in repolarization. Also of note, it is not uncommon to record arrhythmias such as non-sustained ventricular tachycardia, supraventricular tachycardia, pauses, or atrial fibrillation in healthy volunteers receiving placebo during periods of extended ECG monitoring. Therefore, it is critical that expert cardiology advice be sought to confirm any ECG changes and to ascertain the likelihood of a drug-induced arrhythmia versus the background occurrence of this arrhythmia. In such a situation, saving all available ECG data is highly suggested.
- Management of patients with sustained QTcF prolongation should include close monitoring, with ECGs repeated at least hourly until two successive ECGs show resolution of the findings, correction of any electrolyte abnormalities, and possible discontinuation of other concomitant medications that are known to prolong the QT interval. Consultation with a cardiologist or electrophysiologist is recommended to help in the management of such patients.

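### Section 4.5.19 does not order the later ECG that the 500/60 ms QTcF stop needs, and Table 1 footnote a leaves out the Grade 4 limit of Section 4.6.1 (minor)

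*Combined protocol and SAP*

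**What the plan says.** **Repeat ECG.** The trigger in Section 4.5.19 is a QTcF above 500 ms, a rise of more than 60 ms over baseline, or both. The instruction is that "another ECG must be recorded, ideally within the next 5 minutes, and ECG monitoring should continue until QTcF has stabilized on two successive ECGs". The section also asks the investigator to review every tracing, notify the Medical Monitor and look for other risk factors. It does not refer to Section 5.1.3.

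**Stopping.** Table 1 (Section 5.1.3.3) has three QT rows, and Section 5.1.3.4 repeats their criteria:

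- The first row defines its interval: "Sustained (at least two ECG measurements >30 minutes apart) QTcF that is >500 ms and >60 ms longer than the baseline value"
- The second row uses the same leading word but states no interval: "Sustained absolute QTcF that is >515 ms"
- The third row covers torsades, or a new ECG finding that is clinically worrying, with no spacing requirement

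The action in each row is the same: "Unless there is a clear alternative cause other than study drug, discontinue study treatment".

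**After classification.** Section 5.1.3.4 adds: "Management of patients with sustained QTcF prolongation should include close monitoring, with ECGs repeated at least hourly until two successive ECGs show resolution".

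**Resumption.** Footnote a is attached to all three QT rows. It accepts, in rare cases, a restart of azithromycin once the ECG is normal again, with monitoring and after discussion with the Medical Monitor. Section 4.6.1 requires permanent discontinuation for any Grade 4 event judged related to treatment, and the only exclusion it writes is for COPD exacerbations. Appendix 5 puts a cardiac rhythm event that needs treatment in Grade 4.

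**The concern.** The trigger in Section 4.5.19 uses the same two thresholds as the first stopping row, so it is the natural step to feed that stop. Yet a site can complete it without obtaining the pair of tracings by which the stop is judged. Two sites that both follow Section 4.5.19 could then treat the same tracing differently. One takes a later ECG and applies the numeric stop. The other ends monitoring on a stable but still prolonged reading and relies on judgment.

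On resumption, a site that reads only Table 1 after a treated, drug-related arrhythmia could consider a restart that Section 4.6.1 bars. Section 5.1.2.10 itself describes QT prolongation as potentially fatal, so the rules for it should fit together.

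**Working it through.** The plan gives no figure to reproduce. The check compares the texts and does some simple timing arithmetic.

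**1. Time covered by Section 4.5.19**

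Inputs: first prolonged reading at 0 minutes; repeat at 5 minutes (the ideal timing in Section 4.5.19); next ECG *s* minutes later. The protocol does not give *s*, so it is an assumption shown over a range. If both stable ECGs must be repeats, monitoring may end at 5 + *s* minutes.

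| *s* (min) | 5 + *s* (min) | More than 30? |
|---|---|---|
| 5 | 10 | no |
| 10 | 15 | no |
| 15 | 20 | no |
| 25 | 30 | no (equal, not more) |

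The span exceeds 30 minutes only if 5 + *s* > 30, that is, *s* > 25. If the first prolonged reading counts as one of the two stable ECGs, monitoring could end at 5 minutes. These short spans also read *stabilized* as including a plateau above 500 ms. The section does not exclude that, because it names no level.

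**2. Whether another section orders the later ECG**

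The hourly ECGs in Section 5.1.3.4 are for patients whose prolongation is already sustained. They follow that classification and do not establish it. Section 4.3.2 directs sites to the guidance: interruption and "discontinuation for patients who experience adverse events are provided in Section 5.1.3". There the definition implies a later tracing but does not order it.

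**3. Where the first row is the only numeric stop**

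Lower edge = max(500, baseline + 60); upper edge = 515 ms.

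| Baseline QTcF (ms) | Lower edge (ms) | Band (ms) | Width (ms) |
|---|---|---|---|
| 440 or less | 500 | >500 to 515 | 15 |
| 445 | 505 | >505 to 515 | 10 |
| 450 | 510 | >510 to 515 | 5 |

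This assumes a baseline QTcF of at most 450 ms. Section 4.1.2 excludes QTc above 450 ms without naming the correction. If the 515 ms row carries the same spacing, the gap extends above this band, but only by inference from the shared word *sustained*.

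**4. Number of patients**

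About 100 patients randomized 1:1 gives about 50 on azithromycin. Appendix 1 schedules ECGs after baseline at Weeks 24 and 48, and Week 48 ends treatment. Apart from unscheduled and early-termination ECGs, Week 24 is therefore the one scheduled tracing at which this stop can change later dosing: at most about 50 tracings. The documents give no trigger frequency.

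**5. Footnote a against Section 4.6.1**

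- The torsades row stops azithromycin when no other cause is evident.
- Table 3 treats an event as related unless there is evidence of another cause or the timing is implausible. An event stopped under this row would ordinarily be judged related.
- If the arrhythmia needed treatment, Appendix 5 makes it Grade 4.
- Section 4.6.1 then requires permanent discontinuation, while footnote a leaves resumption open and does not mention Section 4.6.1.

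There is no conflict when the event is judged unrelated, or for QTcF prolongation that is not Grade 4.

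**The case against.** The texts are compatible. Section 4.5.19 sets how soon the first repeat is due and puts no upper limit on monitoring. A site that applies the Table 1 definition must take a second ECG more than 30 minutes later, and unscheduled ECGs are allowed. The 5 to 10 minute span depends on an assumed spacing and a loose reading of *stabilized*. All of this stands, and it is why the point is minor. What remains is that the inference is left to the site.

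A reader might infer that a patient with persistent prolongation would simply stay on azithromycin. The documents do not support that. The torsades/new-finding row needs no spacing. The Medical Monitor is told at the trigger. Section 5.1.3.4 says "it is critical that expert cardiology advice be sought to confirm any ECG changes". Section 5.1.3.2 adds that "Study treatment may be temporarily suspended in patients who experience toxicity considered to be related to study drug", and Section 4.6.1 has discretionary stops. These rest on judgment and none orders the later tracing, but they make a missed stop unlikely to go unnoticed.

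A reader might also infer that the protocol permits rechallenge after treated, drug-related torsades. It does not clearly do so. Section 4.6.1 is mandatory and footnote a only permissive, and Section 5.1.3.1 points to Section 4.6.1, which can be read as prevailing. The remaining defect is that footnote a does not say so.

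**Conclusion.** Both inconsistencies are real and minor. First, no section orders the ECG on which the 500/60 ms stop depends. Second, footnote a omits the limit that Section 4.6.1 sets for related Grade 4 events. They concern about 50 patients. Few should trigger, because Section 4.1.2 excludes QTc above 450 ms, known QT prolongation, QT-prolonging drugs and electrolyte disturbance.

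The text comparison needs no numerical assumption. The minutes depend on the assumed ECG spacing, and the millisecond band on a baseline of at most 450 ms. The absence of an interval in the 515 ms row is a matter for optional clarification: in Section 5.1.3.4 the definition can be read as given at first use and carried to the next criterion. No endpoint, sample size or analysis is affected.

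**What to change.** - **Section 4.5.19.** If the repeat ECG still shows QTcF above 500 ms and more than 60 ms over baseline, or above 515 ms, require one further ECG more than 30 minutes after the first prolonged reading before monitoring ends. Cross-refer to Table 1 and Section 5.1.3.4. State that this does not delay an earlier stop on clinical grounds. Do not require it for patients who meet only the 60 ms part of the trigger: a change from 380 to 445 ms is a rise of 65 ms, yet meets neither numeric stop.
- **Table 1, footnote a.** Add: except where Section 4.6.1 requires permanent discontinuation (e.g., a related Grade 4 event such as torsades requiring treatment).
- **Optional.** State in Table 1 and Section 5.1.3.4 whether the 30-minute definition also applies to the 515 ms criterion.

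The cost is a wording amendment and one extra ECG in the few patients who trigger. Appendix 1, footnote k, places ECGs before spirometry, vital signs and blood draws, so these would wait about 30 minutes at that visit unless the extra ECG is exempted from that order.
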